10 STATISTICS AND DATA ANALYSIS

10.1 SAMPLE SIZE CALCULATION

10.1.1 SAMPLE SIZE CALCULATION FOR CML

The sample size calculation is based on A'Hern's Single-Stage Design and the primary outcome measure of molecular response (BCR-ABL or WT1).

A molecular response (BCR-ABL or WT1) rate of 20% would imply the vaccine clearly warrants further investigation. A molecular response rate of 5% or less would be unacceptable and would indicate the vaccine does not warrant further investigation. The probability of obtaining a false positive result, α (i.e. incorrectly accepting for further study a treatment that has a true PFS rate 30%) is set at 10%. The probability of a false negative result, β (i.e. incorrectly rejecting for further study a treatment with a true PFS rate of 50%) is set at 10%. Using these parameters, $\alpha = 0.1$, $\beta=0.1$, p0=5%, p1=20%, 32 HLA A2+ve patients need to be recruited to the study. The drop-out rate is expected to be less than 10%, hence a total of 36 patients will be recruited.

This trial needs to observe a minimum of 4 out of 32 patients who are molecular responders in order to provide evidence that the vaccine warrants further investigation. Patients will be followed up for 2 years to assess molecular response.

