2.1 PRIMARY ENDPOINT

2.1.1 CML:

Molecular response of BCR-ABL (major or minor response or CMR, as defined in section 9.6).

2.1.2 AML:

Time to disease progression. Disease progression in AML is defined as disease relapse.

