10.2 ANALYSIS PLAN

Molecular Analysis

The analyses on molecular response will be performed on all patients with molecular data at a minimum of 2 post-baseline time points (HLA A2 positive patients must also have received at least 1 dose of the vaccine).

Immunological Analysis

To be evaluable for immunological response, positive HLA A2 patients must receive at least 1 dose of the vaccine and the immunological testing must be available until at least week 8 post first dose.

Safety Analysis

For safety analyses, all patients with positive HLA A2 status who received at least one study drug administration will be evaluable for toxicity. All controls will be included in the safety analyses, where relevant.

Other Analysis

For all other analyses, an intention to treat principle will be used.

10.2.1 ANALYSIS FOR CML PATIENTS ONLY:

Primary:

The primary endpoint is molecular response of BCR-ABL (major or minor response or CMR). For the purpose of analysis, response (as defined by section 9.6) will be measured at weeks 4, 8, 12, 16, 20, 32 and 11, 17 and 23 months. Fisher's exact test will be used to compare differences in proportions of molecular response in CML patients versus controls.

Secondary:

The primary analysis will be repeated for major response or CMR of BCR-ABL.

The analysis methods used for BCR-ABL will be repeated for WT1.

Progression free survival, duration of response and overall survival (as defined in Section 2.2) will be estimated using the method of Kaplan and Meier for each group. Survival estimates will be presented with 90% confidence intervals. These endpoints will also be compared between the CML patients and controls using log-rank tests.

Progression free survival for CML patients is defined in Section 2.2 and is measured as the time from date of consent to the study to date of progression or death from any cause. Alive patients who are progression free will be censored at their date of last follow up. Similar analysis will be performed for overall survival and duration of response.

Toxicity will be collected and evaluated according to the NCI CTC toxicity scale (v4.0) and compared between the vaccinated and control groups by Fisher's exact test.

10.2.2 ANALYSIS FOR AML PATIENTS ONLY:

Primary:

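### The CML sample size and 4-of-32 go rule are set on response in BCR-ABL or WT1, with error rates worded as AML PFS rates, while the primary endpoint is BCR-ABL response alone

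*Protocol*

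**What the plan says.** Section 2.1.1 gives the CML primary endpoint as "Molecular response of BCR-ABL (major or minor response or CMR, as defined in section 9.6"). Section 10.2.1 agrees: "The primary endpoint is molecular response of BCR-ABL (major or minor response or CMR"). The synopsis and section 9.5 also name BCR-ABL only. Section 2.2.1 lists WT1 response in CML as a separate secondary endpoint, and section 9.6.1 defines the two responses separately, with different control genes and baseline thresholds.

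Section 10.1.1 differs in two ways.

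- **Endpoint.** The design is an A'Hern single-stage design on the "primary outcome measure of molecular response (BCR-ABL or WT1"). The target is set on the same quantity: "A molecular response (BCR-ABL or WT1) rate of 20% would imply the vaccine clearly warrants further investigation". The lower rate carries no marker: "A molecular response rate of 5% or less would be unacceptable". The pass mark is 4 molecular responders out of 32, again with no marker named.
- **Error rates.** Alpha is described as "incorrectly accepting for further study a treatment that has a true PFS rate 30%) is set at 10" per cent, and beta as the matching error at a true PFS rate of 50%. Those are the AML parameters of section 10.1.2. The next sentence of section 10.1.1 then gives p0 as 5% and p1 as 20%.

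**The concern.** The 4-of-32 count decides whether the vaccine is judged worth further study in CML. The only marker named in the section that sets the count is BCR-ABL or WT1, while everywhere else the primary endpoint is BCR-ABL. A patient with a confirmed WT1 fall and no BCR-ABL response counts under one reading and not under the other. With 3 BCR-ABL responders and 1 such patient, the result is 4 (go) or 3 (no go).

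The rates have the same problem. A reader cannot tell whether 5% and 20% describe BCR-ABL response or response in either marker. A response in either marker is at least as frequent as a response in BCR-ABL, so one pair of rates fits both endpoints only if WT1 adds no responders. The sentences that should say where alpha and beta apply name an endpoint, PFS, that is not primary in CML.

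**Working it through.** **Inputs (section 10.1.1).** p0 = 5%, p1 = 20%, alpha and beta limits 10% each, n = 32, go if at least r = 4 respond.

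**Formula.** With X binomial(32, p), P(go | p) = 1 − Σ C(32,k) p^k (1−p)^(32−k), summed over k = 0 to 3.

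**Step 1: reproduce the plan.**

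- p = 0.05: 1 − (0.1937 + 0.3263 + 0.2662 + 0.1401) = 0.074, so alpha is 7.4%.
- p = 0.20: 1 − (0.0008 + 0.0063 + 0.0246 + 0.0614) = 0.907, so power is 90.7% and beta 9.3%.
- Searching upward over n, 32 with r = 4 is the first design that meets both limits; at n = 31 with r = 4 the power is 89.3%. The stated size and pass mark are therefore correct for 5% against 20%.

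**Step 2: the error rates as worded.** At a true rate of 30% the 4-of-32 rule gives P(go) = 99.5%, not 10%. At 50%, P(no go) is about 0.0001%, not 10%. So the PFS rates cannot have been the inputs. They do fit the AML rule: 16 of 39 at 30%/50% gives alpha 9.4% and power 90.0%.

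**Step 3: what a mismatch would do.** The protocol gives no rate for BCR-ABL alone or WT1 alone, so the rates below are assumptions. The two cases are alternatives; they cannot both hold.

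*Case A. 5% is the BCR-ABL null, but a response in either marker is counted.*

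| Union null rate | P(go) |
|---|---|
| 5% (WT1 adds no responders) | 7.4% |
| 6% | 12.3% |
| 7% | 18.3% |
| 10% | 40.0% |

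The last row is the ceiling if WT1 also has a 5% null (5% + 5%, with no patient responding in both). Independent markers at 5% each would give 1 − 0.95 × 0.95 = 9.75% and P(go) = 38.1%.

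*Case B. 5% and 20% are union rates, but only BCR-ABL responders are counted.*

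| BCR-ABL rate when the union rate is 20% | Power |
|---|---|
| 20% | 90.7% |
| 18% | 85.3% |
| 15% | 72.8% |
| 12.5% | 58.0% |

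In this case the false-go rate does not rise: it is 3.8% at a BCR-ABL null of 4% and 1.5% at 3%.

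**Step 4: consistent use.** If the rates and the count refer to the same endpoint, whichever it is, alpha is 7.4% and power 90.7%, as in step 1.

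**The case against.** Four points can be made for the plan.

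- **The numbers are sound, and the primary endpoint is the same in four other places.** Both true. The PFS phrases are evidently carried over from the AML section and did not enter the calculation. A reader might infer from them that the rule has a 99.5% false-positive rate, or that 32 is wrong; the stated p0 and p1 rule out both.
- **No composite responder is defined.** Section 9.6.1 defines each marker's response separately, and section 10.2.1 repeats the BCR-ABL methods for WT1. The phrase could be loose wording for each marker in turn. That is possible, but section 10.1.1 calls the quantity the primary outcome measure and sets the target rate on it, so the text still has to be settled.
- **The large figures need stacked assumptions.** A reader might infer that an inactive vaccine passes about 40% of the time. That needs 5% to be the BCR-ABL null, a WT1 null also of 5%, and no overlap between responders. Section 9.5 takes both assays from the same blood sample, and section 1.1.3 uses both to assess the same anti-leukaemia effect. Positive association is more plausible, which puts the union null nearer 5%. If 5% was set for the union and the union is counted, there is no inflation at all.
- **The formal comparison in section 10.2.1 is Fisher's exact test against controls.** True, but section 10.1.1 makes the 4-of-32 count the criterion for further investigation, so its definition matters separately.

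**Conclusion.** The point holds as an endpoint inconsistency, not an arithmetic error. Section 10.1.1 states a primary outcome that differs from the synopsis and sections 2.1.1, 9.5 and 10.2.1, and it attaches the CML error rates to AML PFS rates. For 5% against 20% the design of 32 patients and at least 4 responders is correct, with exact alpha 7.4% and power 90.7%. What is missing is any basis for reading 5% and 20% as BCR-ABL rates, so the 10%/10% limits are not established for the primary endpoint. The documents do not show that the limits are breached.

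The size depends on rates that the protocol does not give. Under case A the false-go probability is 12% to 18% for a union null of 6% to 7%, with 40% as a ceiling. Under case B power is 58% to 85% for BCR-ABL rates of 12.5% to 18%. The firm consequence is the ambiguous count: one WT1-only responder can turn 3 into 4, and the choice could be made after the results are known.

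**What to change.** In section 10.1.1:

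1. Name BCR-ABL response (major, minor or CMR, as in section 9.6) as the endpoint for p0, for p1 and for the count of 4 in 32. State that WT1 response is secondary and outside the go rule.
2. Replace the true PFS rates of 30% and 50% in the definitions of alpha and beta by true BCR-ABL response rates of 5% and 20%.
3. Have the sponsor confirm, with the basis, that 5% and 20% are the intended rates for BCR-ABL alone. Relabelling without this step would hide the problem.

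If the sponsor confirms, this is a wording amendment; 32 patients and 4 responders stand. If the rates were set for either marker, restate the alpha and power of the 4-of-32 rule at the BCR-ABL rates. The cost is then one exact binomial calculation and a decision on whether the resulting power is acceptable.

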10.1.2 SAMPLE SIZE CALCULATION FOR AML

The sample size calculation is based on A'Hern's Single-Stage Design and the primary outcome measure of progression free survival (PFS) at 2 years.

A progression free survival rate of 50% at 2 years would imply the vaccine clearly warrants further investigation. A PFS rate of 30% or less at 2 years would be unacceptable and would indicate the vaccine does not warrant further investigation. The probability of obtaining a false positive result, α (i.e. incorrectly accepting for further study a treatment that has a true PFS rate 30%) is set at 10%. The probability of a false negative result, β (i.e. incorrectly rejecting for further study a treatment with a true PFS rate of 50%) is set at 10%. Using these parameters, $\alpha = 0.1$, $\beta=0.1$, p0=30%, p1=50%, 39 HLA A2+ve patients need to be recruited to the study. The drop-out rate is expected to be less than 10% (see section 3.1 for details of patient replacement).

This trial needs to observe a minimum of 16 out of 39 patients who are progression free and alive at 2 years in order to provide evidence that the vaccine warrants further investigation.

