3 TRIAL DESIGN

This is a non-randomised open label, single dose level Phase II study in two patient groups (CML and AML) based on HLA A2 genotype. Consented and eligible HLA A2+ patients will be vaccinated with two DNA vaccines, p.DOM-WT1-37 (epitope sequence: VLDFAPPGA) and p.DOM-WT1-126 (epitope sequence: RMFPNAPYL). Patients with HLA A2-ve genotype will therefore form the unvaccinated control group. The sample size for the HLA A2+ group has been determined using a A'Hern's single stage study design.

Intervention group of HLA A2+ patients:

32 HLA A2 +ve patients with data to at least 16 weeks will be recruited into the CML treatment group.39 HLA A2 +ve patients with data to at least 16 weeks will be recruited into the AML treatment group.

Control groups of HLA A2-negative but otherwise eligible, consenting patients:

CML: Control group: all eligible and consenting patients who are HLA A2 negative AML: Control group: all eligible and consenting patients who are HLA A2 negative

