4.4 WITHDRAWAL CRITERIA

Patients who are removed from the study treatment due to adverse experiences (clinical or laboratory) will be treated and followed according to accepted medical practice. All pertinent information concerning the outcome of such treatment must be recorded in the CRF.

Patients who withdraw their consent from participating in the trial will be withdrawn from protocol procedures. Data that has been collected on these patients to this timepoint will be included in the analyses.

The discontinuation of study treatment will occur under the following circumstances

- Unacceptable toxicity
- Any patient who experiences a WHO CTC grade 3 adverse reaction (AR), possibly or likely to be related to vaccination will discontinue further vaccination.
- Severe local toxicity (CTC 3 or greater) at the site of injection, development of clinically relevant anti-DNA antibodies or rheumatoid factors, clinical or biochemical evidence of muscle destruction (CTC 3 or greater) or other unexpected toxicity will lead to termination of the vaccination of that patient.

- Unforeseen events: any event which in the judgement of the Investigator makes further treatment inadvisable
- SAE requiring discontinuation of treatment
- The patient withdraws consent where a patient is not evaluable, additional patients will be recruited to replace them (See Section 3.1)
- Serious violation of the study protocol (including persistent patient attendance failure and persistent non-compliance)
- Evidence of disease progression
- In patients with CML requirement to discontinue or change the dose of tyrosine kinase inhibitor therapy

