The primary endpoint is time to disease progression measured as the time from date of consent to the study to date of progression or death from any cause (progression is defined as disease relapse). Alive patients who are progression free will be censored at their date of last follow up. Progression free survival will be estimated using the method of Kaplan and Meier for each group. Survival estimates will be presented with 90% confidence intervals. A log rank test will be computed to compare AML patients and their controls.

Secondary:

The primary analysis will be repeated for survival time.

A secondary endpoint is molecular response of WT1 (major or minor response or CMR). For the purpose of analysis, response (as defined in section 9.6) will be measured at weeks 4, 8, 12, 16, 20, 32 and 11, 17 and 23 months. Proportions of responders in the vaccinated group will be compared with the control group using Fisher's exact test for the CML and AML groups. This analysis will be repeated for major molecular response or CMR of WT1.

Toxicity will be collected and evaluated according to the NCI CTC toxicity scale (v4.0) and compared between the vaccinated and control groups by Fisher's exact test.

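### The AML go/no-go count (16 of 39 at 2 years) has its stated 90% power only if 2-year status is known for all 39, and the replacement wording does not clearly cover late losses

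*Protocol*

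**What the plan says.** - **Design (Protocol 10.1.2).** "The sample size calculation is based on A'Hern's Single-Stage Design and the primary outcome measure of progression free survival (PFS) at 2 years". The unacceptable rate is fixed by "A PFS rate of 30% or less at 2 years would be unacceptable", the rate of interest is 50%, and alpha and beta are both 10%.
- **Decision rule (10.1.2).** "This trial needs to observe a minimum of 16 out of 39 patients who are progression free and alive at 2 years".
- **Drop-out, AML (10.1.2).** "The drop-out rate is expected to be less than 10% (see section 3.1 for details of patient replacement"; no larger recruitment figure follows.
- **Drop-out, CML (10.1.1).** For the same expected rate: "The drop-out rate is expected to be less than 10%, hence a total of 36 patients will be recruited".
- **Who the 39 are.** Section 3: "39 HLA A2 +ve patients with data to at least 16 weeks will be recruited into the AML treatment group". The synopsis gives the same number with data to at least 8 weeks.
- **Replacement.** Section 3.1 permits, but does not require, replacement of patients who fail the section 10.2 criteria. Section 4.4, under withdrawal of consent, says that patients who are not evaluable will be replaced and refers back to 3.1. On withdrawn patients it also says: "Data that has been collected on these patients to this timepoint will be included in the analyses".
- **Analysis sets (10.2).** Criteria are given for the molecular, immunological and safety analyses. Everything else, including AML PFS, is by intention to treat.
- **AML primary analysis (10.2.2).** Kaplan-Meier with 90% confidence intervals and a log-rank test: "Alive patients who are progression free will be censored at their date of last follow up".

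**The concern.** A count of patients seen to be progression free at 2 years has the operating characteristics of a binomial with 39 trials only if every one of the 39 has a known status at that time. The protocol expects some drop-out and relies on replacement to deal with it, but no replacement trigger refers to 2-year status. A patient who leaves follow-up at, say, month 12 without relapse has met the 16-week data requirement, breaches no criterion in 10.2, and remains in the intention-to-treat set. That patient can no longer contribute to the 16.

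Two things are at stake. The chance of discarding a vaccine with a true 2-year PFS of 50% can exceed the stated 10%. And the go/no-go count can disagree with the Kaplan-Meier 2-year PFS that the trial will report from the same patients, because one treats late loss as a non-success and the other censors it.

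**Working it through.** **Inputs.** From 10.1.2: n = 39, threshold r = 16, p0 = 0.30, p1 = 0.50, drop-out expected below 10%. From 10.1.1: CML 32 raised to 36.

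**1. The plan's own figure.** With X ~ Bin(39, p):
- power = P(X ≥ 16 | p = 0.50) = 0.9002
- alpha = P(X ≥ 16 | p = 0.30) = 0.0944

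The design reproduces. 39 with threshold 16 is the smallest single-stage design that meets 10%/10%, and power exceeds 90% by only 0.02 percentage points.

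**2. Inflation.**
- CML: 32/0.9 = 35.6, so 36 (applied).
- AML: 39/0.9 = 43.3, so 44 (not applied).

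**3. Unreplaced loss counted as failure.** Let d be the probability that a patient's 2-year status is lost, independent of outcome. The probability of an observed success is p(1 − d), so the rule passes with probability P(Bin(39, p(1 − d)) ≥ 16).

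| d | success probability at p = 0.50 | power | alpha |
|---|---|---|---|
| 0 | 0.500 | 90.0% | 9.4% |
| 2% | 0.490 | 87.6% | 8.1% |
| 5% | 0.475 | 83.4% | 6.3% |
| 8% | 0.460 | 78.3% | 4.9% |
| 10% | 0.450 | 74.4% | 4.0% |

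**4. A fixed number lost, 16 still required.** Whether the lost patients stay in the denominator or are dropped, 16 successes must come from those remaining:
- 38 known: 87.2%
- 37 known: 83.8%
- 36 known: 79.7% (alpha 4.7%)
- 35 known: 75.0% (alpha 3.6%)

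Strictly below 10% of 39 means at most 3 patients (3/39 = 7.7%), that is, 36 known. If the threshold were re-derived for 36 (at least 15), power would be 87.9% and alpha 9.2%, but the protocol does not provide for that.

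**5. The Kaplan-Meier alternative.** With complete follow-up, a 2-year estimate of at least 40% is the same rule as 16 of 39, because 15/39 = 38.5% and 16/39 = 41.0%. I simulated 39 patients with 2-year PFS of 0.50 or 0.30 and 10% non-informative loss by month 24, starting at month 0 or near week 16 (40,000 trials per setting). Weibull shapes of 0.6, 1.0 and 1.5 were assumed, as the protocol gives no PFS distribution.
- Raw count: power about 74-75%, alpha about 4%.
- Kaplan-Meier estimate of at least 40%: power about 88-89%, alpha 9.4-9.8%.

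**The case against.** A reader might infer that the AML cohort simply has 74% power. The documents do not support that, for these reasons, all of which stand.

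- The protocol expects drop-out below 10%; it does not plan for 10%. The 74.4% is the value at the ceiling.
- The drop-out sentence itself refers to replacement, and 4.4 words replacement of non-evaluable patients after withdrawal of consent as definite, with no week-16 limit. If every late loss were replaced, power would stay at 90.0%.
- The 39 are patients with data to at least 8 or 16 weeks, so earlier losses need not use up the 39.
- Stopping vaccination does not end follow-up. Section 4.4 keeps following patients removed for adverse experiences, section 9 follows all patients for up to 36 months, and sections 11.2 and 11.4 keep patients given other treatment in the trial for analysis. Patients who relapse or die before leaving lose no information. The documents do not say what share of drop-out would lose PFS status.
- Section 10.1.2 does not say how a lost patient is scored; counting as failure is an assumption, and a statistical analysis plan could settle it.
- The primary Kaplan-Meier and log-rank analysis already handles censoring, so only the count rule is affected. No stated figure is miscalculated.

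What remains is that the protocol itself fixes the count, the 39, the drop-out expectation and the reference to replacement, and these do not fit together. Evaluability is undefined for 2-year PFS, so the replacement wording in 3.1 and 4.4 cannot be relied on for a patient lost after week 16.

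**Conclusion.** The point holds as an incompletely specified decision rule. Under the protocol's own drop-out expectation, the 90% power is assured only if every loss of 2-year status is replaced, and the text does not secure that. Power lies between about 74% and 90%, according to how many such losses occur and how they are treated. With the most losses that stay strictly below 10% (3 of 39) it is 79.7%. The error runs towards rejecting an active vaccine: alpha falls as well, to 4.0% at 10% loss, so false acceptance is not increased.

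The lower figures assume loss independent of outcome, no replacement after the 8- or 16-week point, and 16 successes still required.

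**What to change.** 1. In 10.1.2, state the AML rule on the estimate already planned in 10.2.2: the vaccine warrants further investigation if the Kaplan-Meier 2-year PFS in the HLA A2+ AML patients is at least 40%. Say that this equals 16 of 39 with complete follow-up, and give its operating characteristics at 10% loss: about 88-89% power and alpha just under 10%, assuming non-informative censoring.
2. If the raw count is kept, state that patients lost before 2 years count as failures, and give power as a range from 90% down to about 74% at 10% loss.
3. Reconcile the replacement wording in 3.1, 4.4 and 10.1.2, and the 8-week (synopsis) and 16-week (section 3) statements, so that replacement is not presented as covering losses after that point.

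Recruiting 44, in line with CML, is another route, but the denominator and threshold must then be fixed too. With all 44 kept in the denominator, 10% counted as failures and the threshold still 16, power is 90.5% but alpha is 11.1%.

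The preferred change is wording only, with no extra patients or data. Its price is a stated power slightly below 90% at 10% loss and reliance on non-informative censoring, which 10.2.2 already assumes.
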